3.5.4 ECG

A single 12-lead ECG will be obtained locally during screening using an ECG machine that automatically calculates the heart rate and measures PR, QRS, and QT intervals. The ECG results will be interpreted locally. Any findings will be recorded in the eCRF.

3.6 Tertiary/exploratory outcome variables

3.6.1 Peak Pruritus Numeric Rating Scale

The Peak Pruritus NRS is a one-item assessment that asks participants to rate the intensity of their worst itch during the past 24 hours. The scale ranges from 0 (no itch) to 10 (worst itch imaginable).

Participants will be asked to record their Peak Pruritus NRS assessment using a handheld device at site at Visit 2, then at home every evening starting the day after Visit 2 thereafter

until Week 72 (Visit 22). Note that this endpoint is not collected during the screening period and so a baseline score will not be available. All changes will be assessed in an exploratory manner, relative to disease control.

Weekly mean scores will be computed for each week starting from the 7th day after disease control. Change will be assessed by comparison to the assessments on the date when disease control was recorded and on the 6 days after as per Section [3.1.1](#).

For each participant, weekly mean scores will be calculated by summing the daily score over the past 7 days. If a daily assessment is missing, the corresponding daily score is missing. If a participant has at least 4 non-missing daily assessments included in the calculation of the weekly score, the weekly mean score is defined as the sum of the available daily assessments in that week, divided by the number of days with non-missing daily assessments. If there are less than 4 non-missing daily assessments included in the calculation of the weekly score, then the weekly mean score is missing for that week.

Binary endpoints will be derived using weekly mean scores, whereby participants will be classified as a responder or a non-responder for each week using pre-specified clinically meaningful thresholds.

As no threshold for a clinically relevant within-person response definition has been established for BP, the ≥ 2 –4-point change threshold proposed for atopic dermatitis by [Yosipovitch et al 2019](#) will be used for this study. Atopic dermatitis is an appropriate comparison point as it is another intensely pruritic inflammatory skin condition associated with eosinophilia ([Jenerowicz et al 2007](#)). Therefore, in the current study, a participant will be considered to have an improvement for a given week if a ≥ 2 -point reduction versus disease control is observed, and will be considered to have a worsening for a given week if a $>=2$ point increase versus disease control is observed for the weekly mean score. However, depending on distribution of the data, other thresholds for response may be explored. Different approaches might also be explored using a response definition based on achievement of an absolute score. The responder definition will be finalized and documented before unblinding.

The set of intercurrent events for this estimand consists of participants who need to increase their OCS dose as a rescue therapy to treat their BP after having previously achieved disease control, those who receive medications deemed to be intercurrent events as per Section [3.1.5.2](#), and those who withdraw from the study.

Participants who receive medications deemed to be intercurrent events as per Section [3.1.5.2](#) will be considered as non-responders from the date of start of restricted medications.

Participants who need to increase their OCS dose as a rescue therapy to treat their BP after having previously achieved disease control will be considered as non-responders from the date of OCS dose increase recorded with start date > date of disease control assessment.

For restricted medications/OCS during the study missing/partial start dates are not allowed.

Participants who withdraw from the study or are lost to follow-up and don't have a change in medications as described above will be considered as non-responders from their last available assessment.

Participants with missing data for any other reason will be considered as non-responders.

For the summary statistics of the weekly mean scores the same approach described for the IGA score in Section 3.4.4 will be applied to handle with intercurrent events and missing data.

Peak Pruritus NRS assessment compliance will be also evaluated for each week until Week 72. Peak Pruritus NRS assessment compliance is defined as the total number of actual completed diary entries divided by the number of diary entries expected for a given time period. For weeks in which a visit is planned, the 7 daily scores prior to that visit will be used for calculating the weekly compliance rates, thus the day of the visit will not be included into the weekly compliance rating.

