**Table 3** **Schedule of PRO Assessments**

Instruments	Schedule
Peak Pruritus Numeric Rating Scale and OCS Usage	First assessment at site at V2, then at home every evening (17:00-23:59) starting the day after V2 at home thereafter until V22 (Week 72). a
BPDAI-Pruritus, AB-QoL, EQ-5D-5L	At site at every visit up to V22 (Week 72), and then every 12 weeks thereafter. At site at unscheduled, IPD, and follow-up visits.

a Participants will complete BPDAI-pruritus, AB-QoL, and EQ-5D-5L onsite using the tablet. Some participants may be exempted from completing the at home PRO assessments on the handheld device (ie, Peak Pruritus Numeric Rating Scale and OCS Usage) upon agreement with the AstraZeneca physician.  
AB-QoL, Autoimmune Bullous Disease Quality of Life; BPDAI, bullous pemphigoid disease area index; EQ-5D-5L, European Quality of Life-5 Dimensions; IPD, investigational product discontinuation; OCS, oral corticosteroids; PRO, patient-reported outcomes; V, visit.

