### **Type of Participant and Disease Characteristics**

- 3 Participants must have clinical features of BP (eg, urticarial or eczematous or erythematous plaques, bullae, pruritus) at the screening visit and confirmed diagnosis with histology, direct immunofluorescence, and serology at randomization. Required for inclusion:
  - (a) Histology.
  - (b) Positive direct immunofluorescence (from skin biopsy) (IgG and/or C3 at the basement membrane zone).
  - (c) AND at least one of the following serologic assessments positive (all assessed from participant's blood sample):
    - (i) indirect immunofluorescence (IgG on the roof of salt- split skin).
    - (ii) positive serology on ELISA for BPAG1 (230-kd).
    - (iii) positive serology on ELISA for BPAG2 (180-kd).
- 4 BPDAI activity score  $\geq 24$  at the screening and randomization visits.
- 5 Candidate for systemic corticosteroid therapy.
- 6 Able to complete PRO assessments on a tablet and on a handheld device. Some participants may be exempted from completing home PROs on the handheld device upon agreement with the AstraZeneca physician (eg, if the patient has a medical condition such as BP lesions of the fingers/hand, a neurologic condition affecting fingers/hand, or severe visual impairment).

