#### **9.4.6.1 Patient-reported Outcomes**

Quality of life will be assessed using the AB-QoL total score and the EQ-5D-5L score at the visits specified in the SoA ([Table 2](#)). For each of these continuous endpoints, observed means and mean changes from baseline will be summarized using descriptive statistics by treatment group and each scheduled visit. To support these summaries, an MMRM model may be fitted to each of these outcome variables if deemed appropriate, following the details outlined in Section [9.4.2.2](#) for BPDAI activity score.

Itch will be assessed using the Peak Pruritus NRS and recorded every day from Visit 2 onwards by participants using a handheld device. Note that this endpoint is not collected during the screening period and so a baseline score will not be available. All changes will be assessed in an exploratory manner, relative to disease control. Analyses of the Peak Pruritus NRS endpoint will be completed in the subset of patients able to use the handheld device.

For each participant, if at least 4 non-missing daily assessments are available in a weekly period, a weekly mean score will be derived starting from the seventh day after disease control, by summing the daily score over the available assessment and dividing by the number of available assessments in that week. If there are less than 4 non-missing daily assessments included in the calculation of the weekly score, the weekly score is missing for that week. The weekly scores will be summarized by descriptive statistics for observed means and mean changes from disease control.

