2.1.2 Full analysis set (FAS)

This analysis set comprises all randomized participants who received at least 1 dose of investigational product (IP), irrespective of their protocol adherence and continued participation in the study. Participants will be analysed according to their randomized treatment irrespective of whether or not they have prematurely discontinued, according to the intention-to-treat (ITT) principle.

All efficacy analyses will be performed using an ITT approach based on the FAS.

Demography and baseline characteristics will be summarized by treatment for the FAS. If there are major differences between the FAS and the safety analysis set, the summaries will be repeated and presented for the safety analysis set.

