4 ANALYSIS METHODS

4.1 General principles

The primary analysis will be based on the initial 36-week, double-blind, placebo-controlled phase of the study, and will compare all participants randomized to benralizumab until Week 36 against all participants randomized to placebo until Week 36.

All personnel involved in the analyses of the study will remain blinded until the primary DBL and protocol deviations are identified.

The current SAP focuses on the double-blind study period with a high-level description of the descriptive analysis for the OLE analysis. If required, additional detail regarding descriptive analyses in the OLE period will be provided in a separate OLE SAP.

The primary CSR will focus on data from the double-blind period as defined in Section [3.1.2](#).
Final data collected during the OLE period will be reported separately.

Efficacy endpoints will be analysed using the FAS, the analysis of safety endpoints will be based on the safety analysis set. Analysis sets are defined in Section [2.1](#).

Summary data will be presented in tabular format by treatment group. Categorical data will be summarized using frequency and percentages, where the denominator for calculation is the underlying analysis set population unless otherwise stated. Continuous data will be summarized with descriptive statistics of number of available observations, mean, standard deviation, median, minimum and maximum, and quartiles where more appropriate. Data listings will be sorted by treatment and participant number.

All point estimates will be presented together with 95% confidence intervals (CIs) as measures of precision and nominal 2-sided p-values, rounded to 4 decimal places.

Hypothesis testing for the primary and key secondary endpoints will be based on a 2-sided test and carried out using a 5% significance level. If a p-value is less than 0.05, the treatment effect favours benralizumab and the decision will be to reject the null hypothesis (H0) and the alternative hypothesis (H1) will be accepted, subject to the testing strategy outlined in Section [4.1.1](#) below. Any p-values presented for endpoints other than those included in the testing strategy will be nominal (i.e. not multiplicity adjusted).

All analyses for the OLE endpoints will be descriptive, as no placebo-control data will be available for this period. Consequently, no hypothesis testing will be performed.

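### The SAP omits the protocol's device-user restriction for Peak Pruritus, so as written it counts device-exempt participants as non-responders every week

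*SAP*

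**What the plan says.** **Protocol.** Inclusion criterion 6 (Section 5.1) lets exempt participants into the trial: "Some participants may be exempted from completing home PROs on the handheld device upon agreement with the AstraZeneca physician". The Table 3 footnote repeats this for the schedule: "Some participants may be exempted from completing the at home PRO assessments on the handheld device". The at-home instruments are the Peak Pruritus NRS and the OCS usage question. BPDAI-Pruritus, AB-QoL and EQ-5D-5L are completed by everyone on the site tablet. Section 8.1.2 places the exemption request before the screening visit. Section 9.4.6.1, as changed by Amendment 3, sets the population: "Analyses of the Peak Pruritus NRS endpoint will be completed in the subset of patients able to use the handheld device".

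**SAP.** Section 3.6.1 describes collection without mentioning exemption: "Participants will be asked to record their Peak Pruritus NRS assessment using a handheld device at site at Visit 2", and then at home every evening. With fewer than four daily entries in a week, "then the weekly mean score is missing for that week". For the binary endpoint, after its rules for intercurrent events and withdrawal, the section says: "Participants with missing data for any other reason will be considered as non-responders". Section 2.1.2 says: "All efficacy analyses will be performed using an ITT approach based on the FAS". Section 4.1 says of percentages that "the denominator for calculation is the underlying analysis set population unless otherwise stated". Section 4.2.10.1 reports the weekly responder proportion by arm as derived in 3.6.1 and names no other population. Section 6, which lists departures from the protocol, has no entry on Peak Pruritus.

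**The concern.** The protocol treats exempt participants as outside this analysis, because the instrument was never given to them at home. The SAP's general rules bring them back in and score the absence of a measurement as absence of response. A programmer working from the SAP would produce a responder proportion with a different denominator from the one the protocol specifies, and nothing in the SAP would flag the difference.

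At stake is how the weekly itch-responder table reads. Each arm's rate would be lower than the rate among those actually measured, by an amount that depends only on how many were exempted. Unequal numbers of exemptions would move the two arms by different amounts.

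**Working it through.** The plan gives no figure for this endpoint, so there is none to reproduce. The check is a comparison of texts followed by a short illustration.

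**Following one exempt participant through the SAP**

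1. The participant is randomized and dosed, and so is in the FAS (SAP 2.1.2).
2. Weekly means start from the seventh day after disease control and need at least four daily scores (SAP 3.6.1). With no home entries, no week qualifies. A single on-site score at Visit 2, if taken, would not change this. The disease-control week used as the reference is missing too.
3. The participant need not have had rescue OCS, restricted medication or withdrawal, so only the catch-all rule for other missing data applies. The result is non-responder, every week.
4. No other denominator is stated, so the participant stays in it (SAP 4.1).
5. SAP 3.6.9 applies the same derivation rules in the open-label extension, to Week 72.

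Under Protocol 9.4.6.1 the same participant is in neither numerator nor denominator.

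**Effect on the reported rate**

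Let p be the response rate among device users and e the exempt share of an arm.

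- Protocol population: reported rate = p
- SAP as written: reported rate = p × (1 − e)

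The documents give neither p nor e. Both are assumed below.

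| Exempt share e | p = 40% | p = 25% |
|---|---|---|
| 5% | 0.40 × 0.95 = 38% | 0.25 × 0.95 = 23.75% |
| 10% | 0.40 × 0.90 = 36% | 0.25 × 0.90 = 22.5% |
| 20% | 0.40 × 0.80 = 32% | 0.25 × 0.80 = 20% |

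**Effect of an imbalance**

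SAP 1.3 plans about 50 per arm. Five extra exemptions in one arm are 5/50 = 10% of it. That arm's rate moves by 0.10 × 40% = 4 points, or 0.10 × 25% = 2.5 points. Treating exemptions in the two arms as independent binomials with 50 per arm, a gap of five or more in either direction has probability of about 4% at 5% exempt, 13% at 10% and 26% at 20%.

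**What is not affected**

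- *Weekly mean scores and changes.* SAP 3.6.1 sends these to the IGA approach in 3.4.4, where values missing for other reasons stay missing. The device-user subset is not stated there either, but no response is imputed.
- *BPDAI-Pruritus.* It is collected on the tablet, with no exemption.
- *Diary compliance.* SAP 3.6.1 divides completed entries by expected entries and does not say whether exempt participants have expected entries. This is unclear rather than wrong.

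**The case against.** The strongest reply is that the SAP never mentions exempt participants. The result above is inferred from three general rules, and the denominator rule gives way where something else is stated. SAP Section 1 says the SAP describes the protocol's analyses and lists changes in Section 6. No change is listed there, so the protocol's restriction could be read as still in force. The omission also looks like version lag. Other Amendment 3 changes were not carried over: urinalysis is still summarized in SAP 3.5.2 and 4.2.9.2, and the steroid-sparing objective remains in SAP Table 1.

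This disposes of one tempting inference, that the SAP deliberately changed the population. Nothing supports that. It does not remove the conflict. If the restriction still applies, the SAP's unqualified missing-data rule contradicts it, and the SAP is the document that will be programmed. Its amendment history has entries dated 18/05/2023, after protocol Amendment 3 of 26 Apr 2022, so there was an opportunity to align the two. The SAP also says the responder definition will be settled before unblinding, but that text concerns thresholds and absolute scores, not who is counted.

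A second reply is that the consequence is small, and this stands. The endpoint is exploratory and outside the testing hierarchy, and SAP 4.2.10.1 plans only descriptive summaries. Exemption is to be requested before screening, so it is balanced between arms in expectation.

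**Conclusion.** The two documents conflict, and the SAP should be corrected. As written, its weekly responder proportion is the device-user rate times (1 − exempt share). That is a relative reduction of 5% to 20% for an assumed exempt share of 5% to 20%, for example 40% reported as 38% down to 32%. Five extra exemptions in an arm of 50 move its rate by 4 points at 40% response and 2.5 points at 25%. The mismatch in the text is certain. The sizes rest wholly on assumed exemption and response rates.

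A reader might go further and infer that the trial's itch result is understated, that a planned treatment difference shrinks, or that the rule favours one arm. The documents do not support these readings. The itch endpoint in the hierarchy is BPDAI-Pruritus, which is untouched. No between-arm estimate or test is planned for Peak Pruritus. A chance imbalance in exemptions adds noise to a descriptive table, not a systematic bias towards either arm. The primary and key secondary results, the type I error rate and power are unaffected.

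**What to change.** In SAP 3.6.1 and 4.2.10.1:

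- define the Peak Pruritus population as FAS participants not exempted from the handheld device, and use it for the responder proportions and for expected diary entries in the compliance summary;
- apply the non-responder rule for missing data only within that population;
- report the number of exempted participants by arm.

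Because exemption is to be settled before screening, leaving these participants out of both numerator and denominator preserves the randomized comparison among device users. The change costs a few lines of SAP text and one exemption flag, for a decision that the site and the sponsor's physician already make. It needs no new data collection and can be made before unblinding.

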3.6.2 Autoimmune Bullous Disease Quality of Life Questionnaire (AB-QoL)

The AB-QoL is a 17-item assessment of the health-related quality of life impact of autoimmune bullous diseases, including BP. The recall period is one week. The participant will complete the AB-QoL on a tablet at the site as per the CSP Table 2.

Table 7 AB-QoL questions and scores

Please choose an option from the right hand column which most closely correlates to how you felt within the last week.
	
Questions	Scores
1. In regards to your blistering disease, does your skin burn, sting or hurt in any way?	
  All the time = 3  Sometimes = 2  Occasionally = 1  Never = 0
2. In regards to your blistering disease, does your skin itch?	
  All the time = 3  Sometimes = 2  Occasionally = 1  Never = 0
3. Have you had to change your clothing because of your blistering disease?	
  I have to be very careful with how tight my clothing is and what materials they are made of – I have had to change what I wear all the time = 3  I have had to change most of the things I wear = 2  I have had to change some of the things I wear = 1  I have never had to change what I wear = 0
4. Do you notice your skin heals slowly?	
  I notice this all the time = 3  I notice this sometimes = 2  I notice this occasionally = 1  I have never had this problem = 0
5. Do you have difficulty bathing or showering because of your blistering disease?	
  All the time = 3  Sometimes = 2  Occasionally = 1  Never = 0
6. In regards to your blistering disease, does your mouth have erosions which are painful?	
  All the time = 3  Sometimes = 2  Occasionally = 1  Never = 0
7. In regards to your blistering disease, do your gums bleed easily?	
  All the time = 3  Sometimes = 2  Occasionally = 1  Never = 0
8. Does your blistering disease result in you having to avoid food or drinks that you enjoy?	
  I can no longer eat any of the foods I used to enjoy = 3  I can eat some of the foods I enjoy = 2  I can eat most of the foods I enjoy = 1  I can eat anything I like = 0

Please choose an option from the right hand column which most closely correlates to how you felt within the last week.
	
Questions	Scores
9. As a result of your blistering disease, are you embarrassed about your appearance?	
  All the time = 3  Sometimes = 2  Occasionally = 1  Never = 0
10. Do you feel depressed or angry because of your blistering disease?	
  All the time = 3  Sometimes = 2  Occasionally = 1  Never = 0
11. Do you feel anxious or cannot relax as a result of your blistering disease?	
  All the time = 3  Sometimes = 2  Occasionally = 1  Never = 0
12. Do you worry that friends and family find your blistering skin condition tiresome?	
  All the time = 3  Sometimes = 2  Occasionally = 1  Never = 0
13. Is your blistering disease causing sexual difficulties?	
  All the time = 3  Sometimes = 2  Occasionally = 1  Never = 0
14. Does your blistering disease affect relationships with friends or loved ones?	
  I have had to end a relationship because of my disease OR I cannot have a relationship because of my disease = 3  Relationships are very difficult = 2  Relationships are a little difficult = 1  This has not affected my relationships = 0
15. Does your blistering disease affect your social life?	
  I cannot go out to socialize any more = 3  I can only go to some social events = 2  I can go to most social events = 1  My social life is not affected = 0
16. Does your blistering disease affect your work or study?	
  Yes, I can no longer work or study = 3  Yes, I find it difficult to work or study = 2  Yes, it is a little harder than before to work or study = 1  No, I am not affected OR this is not applicable = 0
17. Do employers discriminate against you because of your blistering disease?	
  I cannot find a job due to my blistering disease = 3  I have had to change jobs due to my blistering disease = 2  I still have my job but it is more difficult than before = 1  My employers are completely understanding OR this is not applicable = 0

The AB-QoL total score for the assessment is computed summing the scores of the 17 questions.

The set of intercurrent events for this estimand consists of participants who use restricted medications, participants who have their OCS dose increased after disease control and participants who withdraw from the study. For the summary statistics the same approach described for the IGA score in Section 3.4.4 will be applied to handle intercurrent events and missing data.

